**Substudy 1 (Partial Function)**

Primary Endpoints: FEV1, response of iPS cells to Trikafta™ treatment

Secondary Endpoints: Sweat chloride, CFQ-R (quality of life questionnaire), weight gain, safety laboratory evaluation/EKG

OBJECTIVES	ENDPOINTS	JUSTIFICATION FOR ENDPOINTS
Primary		
To determine whether iPS cells differentiated to primary airway epithelia -- and treated with ivacaftor/tezacaftor/elexacaftor in vitro -- can predict clinical responsiveness to Trikafta™ in vivo .	
 
Functional and biological correction of CFTR expressed in iPS cells as judged by short circuit current measurements in monolayers, and western blot analysis
 
Forced expiratory volume in one second (FEV1)
 
	
 
These in vitro tests represent standard functional and biochemical analysis that address CFTR rescue, with direct relevance to the in vivo situation.
 
FEV1 is a conventional endpoint and provides a direct measurement of patient health benefit among individuals with cystic fibrosis
 

Secondary		
To verify safety and establish efficacy of Trikafta™ in enrolled patients.	
 
Sweat chloride testQuality of life survey
 
Standard laboratory tests and other measurements, as well as history and physical examination
 
	
 
Provide supportive information regarding study intervention effect using in vivo measures known to indicate CFTR rescue
 
A well-established tool for monitoring patient benefit in cystic fibrosis
 
Confirm safety of the FDA-approved drug
 

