#### 11. Statistical Methods For a proposed open-label prospective 4-week trial of Trikafta™.

**Substudy 1:** Patients with CF or CFTR-dependent illness who do not have access to modulator therapy but exhibit a clinical phenotype suggestive of partial/residual CFTR activity.

We will serially evaluate clinical outcomes of interest prior to and after the start of therapy. Change in clinical measurements (spirometry, weight/BMI, quality of life, sweat chloride) will be monitored. Our main goals are to determine the clinical response to Trikafta™ and to determine if *in vitro* responsiveness of iPS cells predicts clinical response. The primary outcome is response to Trikafta™ after 4 weeks of treatment. In this study a clinical response to Trikafta™ at week 4 of treatment will be defined as an improvement, from baseline, in  $FEV_1 > 5\%$  predicted and each subject will be classified a responder or non-responder. In this study, if at least 40% of subjects meet the definition of responder, the drug will be considered efficacious (i.e., comparable to the benefit which led to Orkambi™ approval by FDA following trials in F508del homozygotes). Overall response rate will be accompanied by an approximate binomial 95% confidence interval. To determine the role of iPS *in-vitro* response to Trikafta™, we will compare the  $\Delta Isc$  (change in  $Isc$ ) among Trikafta™ responders and Trikafta™ non-responders using a two-sample t-test or a Wilcoxon rank sum test if distributions are skewed. Additionally, we will correlate the  $\Delta Isc$  obtained from *in vitro* experiments with the change in  $FEV_1\%$  predicted (post minus pre) using Spearman's rank-order correlation with an associated 95% confidence interval. We will also test whether the iPS response reaches a CFTR functional threshold of 40% wild-type levels (a magnitude of activity in primary airway epithelial cells viewed as potentially relevant to clinical benefit). In a sensitivity analysis, we will replicate the  $FEV_1$  analysis with sweat chloride responses, and determine the *in vivo* response rate.

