For other outcomes of interest including sweat chloride levels, quality of life, and weight/BMI, we will apply a mixed effect model to examine the change in these measures over the study duration. Models will include a subject-specific intercept, to account for variability among subjects prior to the start of the treatment, and a categorical variable for time (baseline, day 14, day 28, day 56). A Dunnet's post-hoc comparisons procedure will be used to determine which time points demonstrated a significant change from baseline. Using the same mixed effects models, we will include  $\Delta Isc$  as predictors of *in vivo* improvement. We will also test the interaction between time and  $\Delta Isc$  to determine when *in-vitro* response is most associated with change in clinical response. Adverse events and other safety endpoints will be tabulated and reported using counts and percentages or means and standard deviations, as appropriate.

In addition, because clinical parameters may vary among patients prior to the start of therapy, we will also approach the analysis using a modified N of 1 design configured for the purpose of comparing iPS studies in contrast to the aggregate analysis described above. Using the framework of single subject research, we will evaluate therapeutic response in individual subjects by an interrupted time series (ITS) approach. Briefly, in the absence of an independent control group, ITS analysis is a quasi-experimental design in which each subject acts as their own control and is followed serially in time prior to and after an interruption (in this case, the start of treatment). If the treatment has causal

impact, the post-intervention time series will have a different level or slope than the pre-intervention series. Time series models also have the power to test and correct for possible cyclical patterns and outliers. Using segmented regression analysis, we will conduct ITS models for each of the subjects enrolled in the trial. A significant change in slope from the pre-treatment period will indicate a significant treatment effect. ITS models will be constructed for each outcome of interest where historical and pre-treatment data are available. The change in slope will also be correlated with the *in-vitro* response using Spearman's rank-order correlation coefficient.

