All analyses will be conducted using the intention to treat principal, where all subjects will be included in analysis regardless of how long they took the study medication. Statistical significance will be assessed at the 0.05 level and analyses conducted using SAS v. 9.4 (SAS Institute; Cary, NC).

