#### Sample size

The FDA has suggested that scientifically meaningful 'binning' of patients based on clinical characteristics can help guide future approval of specific patient groups for drug treatment. The present study is not intended for FDA submission or label expansion of Trikafta™, but as a means to determine whether iPS cells differentiated to respiratory phenotype can be used to predict clinical response to CFTR modulators. For the purposes of this protocol, the subjects enrolled, although potentially of different genotypes, will represent a scientifically meaningful cohort or 'bin' of individuals with partial function mutations, sweat chloride < 80 mmol/L, and/or pancreatic sufficiency. This protocol is designed to compare *in vitro* responsiveness of differentiated iPS cells to *in vivo* clinical activity of Trikafta™, and will test the null hypothesis that the true Trikafta™ response rate of CFTR individuals with partial function mutation genotypes is  $\leq 10\%$  vs. the alternative hypothesis that the true Trikafta™ response rate is  $\geq 40\%$ . We will initially enroll four subjects, and expect all of these individuals will show a clinical response (e.g.,  $> 5\%$  improvement of % predicted FEV1 from baseline). If none of the first four subjects exhibit a response, the study will be terminated. Otherwise, we intend to enroll a total sample size of 22 individuals. Subjects who do not complete the study will be replaced. In this design, if Trikafta™ is ineffective, the probability of early termination after four subjects is 66% and only a 5% chance of concluding the drug is effective (type I error). If Trikafta™ is effective, there is an 86.4% chance of reaching this conclusion. If fewer than four patients show a clinical effect, Trikafta™ will be considered ineffective. To demonstrate the ability of iPS cells to predict clinical benefit, 22 patients will provide at least 80% power to detect a significant correlation of at least  $r = 0.55$  between the changes in clinical outcomes with changes in short circuit current as measured in iPS cells. Tabular details of this analysis are provided below. Power calculations were performed using PASS v. 14 (Kaysville, UT) with a two-sided Z-test and a significance level of 0.05.

	Cumulative # of responses	Decision	95% Confidence Interval (CI)

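### Substudy 1 tests whether iPS response predicts FEV1 response in two overlapping ways, each at 0.05, without formally saying which one decides; the chance of at least one false positive is about 8%, not 5%.

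*Combined protocol and SAP*

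**What the plan says.** Section 4 lists for Substudy 1: "Primary Endpoints: FEV 1 , response of iPS cells to Trikafta™ treatment". The primary objective there is whether iPS-derived airway cells treated in vitro can predict the clinical response.

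Section 11, Substudy 1, examines this on FEV1 in two ways:
- Delta-Isc is compared between responders (FEV1 gain above 5% predicted at week 4) and non-responders, "using a two-sample t-test or a Wilcoxon rank sum test if distributions are skewed".
- As an addition, delta-Isc is correlated with the change in FEV1 % predicted, "using Spearman's rank-order correlation with an associated 95% confidence interval".

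Further analyses of delta-Isc follow:
- For sweat chloride the text says "In a sensitivity analysis, we will replicate the" FEV1 analysis.
- For the other outcomes: "Using the same mixed effects models, we will include" delta-Isc as a predictor, with a time interaction.
- The slope change from the interrupted time series (ITS) models is also correlated with the in vitro response.

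One sentence sets the level for all of these: "Statistical significance will be assessed at the 0.05 level". The only multiplicity procedure is Dunnett's, which covers time points against baseline. The Sample size subsection powers the iPS aim on a correlation alone: at least 80% power at r = 0.55 with 22 subjects, "with a two-sided Z-test and a significance level of 0.05".

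**The concern.** The responder comparison is the correlation with FEV1 change cut into two groups. The two tests share most of their information but need not agree, and at this sample size they often will not. If one is significant and the other is not, the plan does not say which is the answer to the primary iPS question. The 0.05 level then holds for each test but not for the conclusion.

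Section 10 promises a high level of rigour and foresees sharing the results with the manufacturer, insurers, the CF Foundation and patients. It also lists the primary endpoint having been met as a possible reason to end the study. Both need one criterion that can be read without choice. Substudy 2, by contrast, names one primary clinical analysis with its own level.

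**Working it through.** **Inputs from the documents.** n = 22 ("we intend to enroll a total sample size of 22 individuals"); level 0.05, two-sided as in the power statement; r = 0.55; a responder share of 40%, the plan's efficacy benchmark, varied from 10% to 64%.

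**Assumptions.** All 22 subjects have evaluable iPS data. Delta-Isc is normal, or skewed as a variant. The correlation between FEV1 change and sweat chloride change is not given, so it was varied from 0 to 0.9.

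**Step 1: the plan's own figure.** Power for a correlation at r = 0.55, n = 22, two-sided 0.05:
- Fisher z: atanh(0.55) × √(22 − 3) − 1.96 = 0.618 × 4.359 − 1.96 = 0.736, so power is 76.9%.
- Pearson t-test, 100,000 simulated trials: 79.0%, in line with the stated 80%.
- Spearman, the test actually planned, simulated with bivariate normal data: about 72%. Dividing n − 3 by 1.06 in the Fisher formula, as a Spearman approximation, gives 74.5%. Both are below 80%.

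The stated power therefore fits a Pearson correlation, not the planned Spearman test.

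**Step 2: the two FEV1 tests when there is no association.** Delta-Isc was simulated independently of FEV1 change (40,000 to 100,000 trials per setting).

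| Quantity | Result |
|---|---|
| Spearman alone | 5.0–5.3% |
| t-test or Spearman, 40% responders | 7.8–8.2% |
| t-test or Spearman, 10–64% responders, normal delta-Isc | 7.7–8.7% |
| Wilcoxon or Spearman | 7.1–7.9% |
| t-test or Spearman, favourable direction only | about 4% |

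Two independent tests would give 1 − 0.95² = 9.75%. The overlap between the tests brings this down to about 8%. In the favourable direction the nominal rate is 0.05 / 2 = 2.5%, so the inflation is 4 / 2.5 = 1.6-fold.

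**Step 3: how often the two tests disagree.** In one run at 40% responders, the t-test was significant in 4.94% of trials, Spearman in 5.05% and either in 7.79%. Both were therefore significant in 4.94 + 5.05 − 7.79 = 2.20%. Exactly one was significant in 7.79 − 2.20 = 5.59%, which is 5.59 / 7.79 = 72% of the trials with any false positive.

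**Step 4: if the sweat chloride repeats also counted.** Both tests are repeated on sweat chloride (four tests in all, t-test version, normal delta-Isc, 40% responders):

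| FEV1–sweat chloride correlation | At least one significant |
|---|---|
| 0 | 15.4% |
| 0.3 | 14.8% |
| 0.5 | 14.4% |
| 0.7 | 13.5% |
| 0.9 | 11.9% |

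At 20% responders and zero correlation it is 16.3–16.6%, or 17.2% with skewed delta-Isc. The range is thus roughly 12–17%, and 6–8% in the favourable direction. Independence would give 1 − 0.95⁴ = 18.5%.

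**Step 5: after the fix.** With only the FEV1 Spearman correlation decisive, the rate is about 5%. Keeping both FEV1 tests at 0.025 each gives about 4.2%.

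**The case against.** The best reply is that the plan already points to the correlation. The Sample size text powers the iPS aim on nothing else, and the opening summary, Section 10 and Expected Outcomes all frame the aim as a correlation. A reader might infer that the plan gives no indication at all of a main test; these places do not support that. The indication stays implicit, however. Section 11 puts the responder comparison first and brings in the correlation as an addition, while the Sample size text refers to clinical outcomes in the plural without naming FEV1.

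A reader might also infer that the false-positive rate for the primary claim is 15% or more. The documents do not support that either. Section 11 calls the sweat chloride repeat a sensitivity analysis, Section 4 makes sweat chloride secondary in Substudy 1, and the text does not state outright that both iPS tests are repeated. The 12–17% applies only if a sweat chloride result alone would be claimed as proof of prediction.

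Three further limits stand:
- No rule says that any significant result suffices. Expected Outcomes speaks of a strong correlation in both substudies.
- A significant association in the wrong direction cannot support a claim of prediction, so about 4% is the relevant false-claim rate for the FEV1 pair.
- The choice between t-test and Wilcoxon selects one test by distribution shape; it does not give two attempts.

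The consequence is also limited: the trial is described as a pilot and is not meant for FDA submission or label expansion.

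**Conclusion.** The point holds for the two FEV1 tests. They address one primary question at 0.05 each with no formally named decider, which gives about 8% two-sided instead of 5%, or about 4% instead of 2.5% in the favourable direction. This rests on n = 22, independence of delta-Isc and FEV1 change under the null, and either test being accepted as an answer. It varies little with the responder share.

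The larger 12–17% is conditional on promoting a labelled sensitivity analysis and on a correlation and responder share that must be assumed; it should not be the headline. The mixed-model and ITS analyses of delta-Isc were not counted. They would add to the total only if they too were used as grounds for a claim. The inflation is modest and the remedy simple, so this is a clarification worth making rather than a flaw in the design.

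**What to change.** In Section 11, Substudy 1, state that the single decisive test of iPS prediction is the Spearman correlation of delta-Isc with the Day 28 change from baseline in FEV1 % predicted, at two-sided 0.05. State that the responder/non-responder comparison, the delta-Isc terms in the mixed models and the ITS correlation are supportive and are reported with confidence intervals. The sweat chloride repeat can keep its label as a sensitivity analysis.

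In the Sample size subsection, name FEV1 as the outcome of the powered correlation and restate the power for Spearman: about 72–73% at r = 0.55 with 22 subjects, not at least 80%.

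The cost is a few sentences. No visit, sample or subject is added, and the decisive test keeps the full 0.05. Splitting the level between the two FEV1 tests would also control the error, but each would then be tested at 0.025, with less power than the correlation has at 0.05.

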Cystic Fibrosis (CF) is a life threatening genetic disorder resulting from mutations found in the gene known as the cystic fibrosis transmembrane conductance regulator (CFTR). Defects in this gene prevent correct chloride and bicarbonate transport in and out of cells. It has become increasingly important to develop new *in vitro* model systems capable of predicting *in vivo* clinical effectiveness of modulator therapy among patients with CF. This objective represents a significant and unmet need for advancing personalized therapeutics in the disease. The current trial is intended to show for the first time that primary iPS cells differentiated to an airway epithelial phenotype can be used to predict *in vivo* clinical response for rare CF patient populations – with the long-term goal of facilitating drug access for individuals with unusual (or even private) CF variants. Trikafta™ is currently approved for patients with CF carrying at least one copy of the common F508del variant and over 170 other CFTR abnormalities. In this protocol, we describe a clinical study of 42 subjects without the F508del mutation, carrying partial function or N1303K mutations not approved for Trikafta™, and who are not expected to be approved for CFTR modulator treatment in the immediate future. Each patient will have clinical and/or preclinical evidence that Trikafta™ should offer benefit, and each will be given Trikafta™ for approximately four weeks. We will monitor clinical endpoints that include FEV1 and sweat chloride. We will differentiate iPS cells from each subject to generate airway epithelial monolayers that can be tested for response to Trikafta™. In this way, this study will evaluate an emerging and readily accessible *in vitro* surrogate endpoint as a predictor of clinical response. Our trial will also serve as a pilot/test case for other clinical protocols relevant to patients with rare CFTR variants and evidence of modulator responsiveness who do not have an approved modulator therapy—due to rarity of their mutation. We hypothesize that a robust correlation will be established between *in vitro* Trikafta™ responsiveness of iPS cells and *in vivo* benefit (FEV1) in patients, and providing a powerful tool for utilizing iPS cells to identify rare CF patient populations most suitable for cystic fibrosis modulator therapy.

3. Introduction and Background: A summary of the primary hypothesis, purpose, scholarly rationale, and prior literature.

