
**Figure 1.** Activity of N1303K CFTR in FRT, iPSC, and primary nasal cells. **Panel A:** depicts short circuit current response to elexacaftor/tezacaftor/ivacaftor (ETI) in FRT cells stably expressing the N1303K variant. Note that activation of ~ 10% wildtype level has been viewed as predictive of clinical benefit in the FRT cell system advanced by Vertex Pharmaceuticals. N1303K activity shown here is > 25% wildtype levels. **Panel B:** Western blot indicating enhancement of N1303K bands B and C by ETI. **Panel C:** Transepithelial chloride transport on skin fibroblast derived iPS cells with airway epithelial differentiation. **Panel D:** summary data using the same protocol. Triple combination therapy (TCT) indicates 5-7  $\mu\text{A}/\text{cm}^2$  short circuit current, which is similar to the level of activity obtained using ivacaftor in G551D airway epithelial monolayers derived from iPSCs. **Panel E:** Western blot from an iPSC/N1303K experiment of this sort. **Panel F:** indicates ~ 5  $\mu\text{A}/\text{cm}^2$  in primary nasal airway epithelial monolayers following ETI therapy. This level is in a range that might be predictive of clinical benefit in some settings.

[figure not shown]
As above, poor access comprises a commonplace barrier to optimal care throughout CF clinics in the United States and abroad. The same issue is a major impediment to personalized treatments in diseases such as cancer and HIV infection (Menon et al., 2015; Evans et al., 2015; Nardini, 2014; Jabbour et al., 2015; Lammers et al., 2014). As a result, FDA has sought *in vitro* model systems that could serve as surrogates for clinical benefit among patients with very rare (or even private) alleles and for whom traditional, late-phase clinical testing would be difficult. Preliminary evidence suggests differentiated iPS cells may be an excellent candidate in this regard (Crane et al., 2015; Mou et al., 2015).

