As part of an evaluation to test the relationship between CFTR activity and modulator effectiveness, we worked with 43 rare CFTR variants stably expressed from a single site in the genome of the human CF bronchial epithelia cell line (CFBE41o-) (Han et al., 2018). The magnitude of drug response in these cell models was highly correlated with residual CFTR function for the potentiator ivacaftor, the corrector lumacaftor, and ivacaftor-lumacaftor combination therapy. Response of a second set of 16 variants expressed stably in FRT cells showed similar correlation (although certain variants were identified that demonstrate significantly higher response to modulator treatment than predicted by *in vitro* analysis). In addition, nearly all variants studied in CFBE (40/43) and FRT cells (13/16) demonstrated greater response to ivacaftor-lumacaftor combination therapy than either drug alone. Together, the variants studied here represent 87% of individuals in the CFTR2 database with at least one missense defect. Our results therefore indicate that most patients with CF carrying missense variants are likely to: 1) respond modestly to current potentiator and/or corrector therapy, while a small fraction will exhibit more pronounced CFTR rescue and 2) derive the greatest benefit from combination treatment.

**Overview** FDA has indicated new *in vitro* model systems capable of predicting *in vivo* clinical benefit may represent a significant and unmet need for advancing personalized CF therapeutics. The present study is designed to specifically and prospectively test iPS cells taken from patients encoding rare CF variants as a means to determine *in vitro* thresholds for CFTR rescue. Using iPS cells differentiated to exhibit a respiratory epithelial phenotype, we will determine whether the cells can be used to predict FEV1 response among individuals carrying rare, partial function mutations who receive

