#### Sample Size

With a sample size of 20 participants, we anticipate 99% power to detect a mean sweat chloride decrease of 10 mmol/L assuming a standard deviation of 9.7 mmol/L (Boyle et al., 2014; Vermeulen et al., 2017) under a one-sided 0.025 alpha-level t-test. With a higher standard deviation of 15 mmol/L, the power decreases to 81% to detect a mean decrease of 10, but we retain 98.9% power to detect the hypothesized mean decrease of 15 mmol/L.

SAEs and AEs will be tabulated using standard coding terms sorted by System Organ Class (SOC). The incidence of AEs will be tabulated by seriousness and severity. The number of SAEs and AEs will be

summarized as follows: (i) The proportion of subjects with at least one (S)AE, (ii) The average number of (S)AEs per subject, and (iii) The rate of (S)AEs per subject week of follow-up.

**Expected Outcomes** Subjects will be recruited by study investigators as above, including through the CF Foundation Therapeutic Development Network resource. Please note that based on considerable past experience conducting clinical trials involving CF subjects at both participating institutions, we do not have concerns regarding our ability to perform the patient-oriented study described here, or to propagate and characterize iPS cells (Crane et al., 2015; Mou et al., 2015; Hawkins et al., 2017; Jacob et al., 2017). The protocol will furnish one test of our hypothesis that thresholds of CFTR activity in differentiated iPS cells encoding partial function mutations *in vitro* or *in vivo* predict benefit following Trikafta™ *in vivo*. If a strong correlation can be established between Trikafta™ response *in vitro* and *in vivo* (e.g., FEV1) in both substudies, the clinical results will provide early evidence for possible usefulness of *in vitro* surrogate models in this setting.

**Scientific Rigor** All *in vitro* and *in vivo* studies will be conducted with appropriate “n” so that therapeutically relevant conclusions can be drawn. Multiple biologic or technical replicates will be performed and evaluated in blinded fashion by an experienced statistician. CFTR mutations are equally prevalent in both sexes, and we expect iPS cells studied in human subjects carrying partial function mutations will reflect male and female individuals equally.

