**Summary** Many CF patients who might substantially benefit from new and precise modulator treatments do not have access to these drugs. Off-label prescribing of expensive new agents is often not reimbursed by third-party payers. This project will test new *in vitro* predictive thresholds using iPS cells for CFTR rescue *in vivo*, and furnish a body of knowledge relevant to such issues among individuals with rare or even private CF alleles. We will also specifically evaluate patients with CF encoding N1303K for evidence of clinical benefit attributable to Trikafta™.

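### One of the protocol's two wordings of its iPS hypothesis is that an activity threshold predicts benefit, and no planned analysis relates any threshold to clinical response

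*Combined protocol and SAP*

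**What the plan says.** **Correlation wording.** The opening abstract says "We hypothesize that a robust correlation will be established between" in vitro iPS responsiveness and FEV1 benefit. Section 10 also describes the goal as a correlation. The Substudy 1 sample-size text powers the iPS aim on a correlation of 0.55.

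**Threshold wording.** This appears in three places:
- Section 3, Overview: iPS cells are to be tested as a means of finding in vitro "thresholds for CFTR rescue".
- Section 11, Expected Outcomes: "The protocol will furnish one test of our hypothesis that thresholds of CFTR activity in differentiated iPS cells" predict benefit from the drug.
- Section 11, Summary: the project will test new "predictive thresholds using iPS cells for CFTR rescue" in vivo.

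**Analysis of the threshold.** Substudy 1 has one sentence: "We will also test whether the iPS response reaches a CFTR functional threshold of 40% wild-type levels". The figure is justified in brackets as "a magnitude of activity in primary airway epithelial cells viewed as potentially relevant to clinical benefit".

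**Analyses linking iPS response to outcome.**
- Substudy 1: comparison of the change in short circuit current (ΔIsc) between FEV1 responders and non-responders; a Spearman correlation with FEV1 change; mixed models with ΔIsc and its interaction with time; and a correlation with the interrupted-time-series slope change.
- Substudy 2: Spearman correlations, with fitted curves and each participant's paired values plotted.

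**The concern.** A correlation or a difference in means shows that iPS response and clinical response move together. It does not show that a particular cut-off separates responders from non-responders. The 40% sentence does not fill that gap. As written, it could be met by all 22 subjects, or by none, and say nothing about prediction.

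The protocol intends to share its results with the manufacturer, insurers, the CF Foundation and families, to guide further iPS work. A reader who has been promised predictive thresholds may take a significant correlation, reported beside a statement that iPS currents reached 40% of wild type, as evidence that 40% is a usable cut-off. The planned analyses could not support that. Without a pre-specified threshold analysis, a cut-off could also be chosen after the data are seen.

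**Working it through.** **1. The plan's own figure for the iPS aim.** The only stated power is at least 80% to detect r = 0.55 with N = 22, two-sided 0.05.
- Plain Fisher z: Φ(atanh(0.55)·√19 − 1.96) = Φ(0.618 × 4.359 − 1.96) = Φ(0.735) = 76.9%.
- With the bias term r/(2(n−1)) = 0.55/42: 78.6%. Simulated Pearson t-test (20,000 runs): 78.9%.
- For the planned Spearman test: 74.5% (variance factor 1.06), or 72.4% simulated at an underlying Pearson r of 0.55.

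The stated figure is roughly reproduced for a Pearson test and is lower for Spearman. This is context only. The plan gives no power or precision figure for the threshold analysis, so there is none to reproduce.

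**2. Wordings against analyses.**

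| Wording | Where | Matching analysis |
|---|---|---|
| Correlation of iPS and clinical response | Abstract; section 10; Substudy 1 sample size | Responder comparison, Spearman, mixed models, slope-change correlation |
| Threshold predicts benefit | Expected Outcomes | None |
| Thresholds for CFTR rescue | Overview; Summary | 40% sentence only; no clinical variable named |

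**3. Can the correlation stand in for a threshold?** Illustrative assumptions: bivariate normality, r = 0.55, and the top 9/22 of FEV1 changes counted as responders (0.40 × 22 = 8.8, rounded to 9). The AUC is then about 0.76. The correlation is the same in every row below:

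| Cut-off on ΔIsc | Sensitivity | Specificity |
|---|---|---|
| 5th percentile | 99% | 8% |
| Median | 72% | 65% |
| 95th percentile | 10% | 99% |

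Where 40% of wild type would fall on this scale is not known. The documents take 40% from primary airway cells. The Figure 1 legend gives a different value for another system: "activation of ~ 10% wildtype level has been viewed as predictive of clinical benefit in the FRT cell system". The text defines no wild-type iPS reference.

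**4. What the missing analysis would deliver.** Assumed counts: 9 responders and 13 non-responders.
- Sensitivity 7/9 = 78%, Clopper-Pearson 95% CI 40% to 97%.
- Specificity 10/13 = 77%, 95% CI 46% to 95%.
- Hanley-McNeil standard error for an AUC of A = 0.80, with Q₁ = A/(2−A) = 0.667 and Q₂ = 2A²/(1+A) = 0.711: √{[0.16 + 8(0.667−0.64) + 12(0.711−0.64)]/117} = 0.102.
- Fisher exact test at two-sided 0.05, by full enumeration with 8, 11 or 14 of 22 above the threshold: power 32–36% for response rates of 60% v 20%, 52–54% for 70% v 20%, 73% for 80% v 20%, and 90–91% for 80% v 10%.
- Degenerate case, all 22 above the threshold: sensitivity 9/9 (lower limit 0.025^(1/9) = 66%) and specificity 0/13 (upper limit 1 − 0.025^(1/13) = 25%). The table then carries no information on discrimination.

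**The case against.** A reader might infer that the study's hypothesis goes untested. The documents do not support that. The abstract, section 10 and the power calculation all frame the aim as a correlation. The primary objective in section 4 asks whether iPS cells can predict clinical responsiveness and mentions no threshold. The sentence after the threshold hypothesis in Expected Outcomes itself returns to a strong correlation. The planned analyses address all of these.

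Four further points can be made for the plan:
- The Overview and Summary speak of thresholds for CFTR rescue. Only Expected Outcomes ties a threshold to benefit, and it claims no more than early evidence. This stands, and it narrows the point.
- If the rank-sum test is used, the AUC is already implicit, since AUC = U/(n₁n₂). This holds for overall discrimination. But the rank-sum test is planned only for skewed data, no AUC or interval is to be reported, and nothing describes performance at a cut-off.
- The 40% sentence sits among analyses of clinical response and may have been meant to join them. It might be read as a test of the cells alone, but the text settles neither reading: it gives no unit, method or outcome. The safer description is that it is under-specified.
- With 22 subjects any cut-off is poorly estimated. That is true, and it argues for labelling the result as estimation. It does not justify leaving the promised quantity out.

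**Conclusion.** The point holds in a limited form. One of two wordings of the iPS hypothesis, the threshold wording, has no matching analysis. The single threshold test is under-specified and borrows its 40% value from another cell type. The correlation wording is covered, and the FEV1 and sweat chloride efficacy analyses are unaffected.

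The mismatch follows from the text and needs no assumption. Its practical size cannot be computed from the documents. The sensitivity, specificity, AUC and power figures above rest on assumed counts and rates, and serve only to show how imprecise the added analysis would be. This is a low-cost improvement, best made before outcome and iPS data are compared.

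**What to change.** Either of two changes resolves the mismatch.

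**Tie the 40% test to outcome.** In section 11, Substudy 1:
- Define the wild-type reference for iPS-derived monolayers, and how replicates are combined into one value per subject.
- Cross-classify each subject as at or above 40% of that reference (yes/no) against the FEV1 responder status already defined. Report sensitivity and specificity with exact 95% confidence intervals, labelled as estimation.
- Report the AUC of ΔIsc with its confidence interval beside the planned comparison of responders and non-responders.
- Label any cut-off chosen from the data as exploratory.

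**Or restate the aim.** Reword the Overview, Expected Outcomes and Summary as a correlation aim, and draw no threshold conclusion.

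The first option needs no new subjects or visits, because the plan already calls for both the responder status and the comparison with 40%. Its cost is wide intervals, and a table that tells nothing if nearly all or no subjects reach 40%. The second costs only wording, but gives up the threshold claim.
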